7.1 Clinical Evaluation

7.2 Medical record

The clinical evaluation will be carried out by a rheumatology specialist, who will perform a general physical examination and apply clinical evaluation indices such as:

DAS28 Clinical Activity Index : This index measures disease activity in patients with rheumatoid arthritis (RA). It is calculated using four variables: the red blood cell sedimentation rate (ESR), the number of swollen joints, the number of painful joints (evaluating a total of 28 joints), and a visual analog pain scale. A mathematical formula is then applied, providing a score from 0 to 10. A value greater than 5.1 indicates high disease activity, a value less than 3.2 indicates low activity, and a value less than 2.6 indicates disease remission.

SDAI (Simplified Disease Activity Index): The SDAI is a more simplified disease activity index compared to the DAS28. It is based on five parameters: the number of swollen joints, the number of tender joints, the visual analogue pain scale score, the ESR (or C-reactive protein), and the patient's global status. The total score can range from 0 to 86, and like the DAS28, values above 26.0 indicate high disease activity, while values below 3.3 reflect disease remission.

CDAI (Clinical Disease Activity Index): The CDAI is similar to the SDAI, but differs in that it does not include laboratory measurements, i.e., it does not use ESR or C-reactive protein. It is

calculated by adding the following parameters: number of swollen joints, number of tender joints, the score on the visual analog pain scale, and the patient's overall condition. The total score ranges from 0 to 76, and like the SDAI, values less than 10 indicate disease remission, while values greater than 22.0 indicate high disease activity.

HAQ-DI (Health Assessment Questionnaire Disability Index): The HAQ-DI is a tool used to measure the level of physical disability in patients with chronic diseases, such as rheumatoid arthritis. It assesses a patient's functional ability in eight categories: dressing, bathing, eating, getting out of bed, walking, reaching, bending, and performing activities of daily living. Each category is scored from 0 to 3 (with 0 being no difficulty and 3 being maximum difficulty), and the total score is obtained by adding the scores for each category and dividing by the total number of categories assessed. A higher score indicates greater functional disability.

7.3 24-hour reminder

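### Protocol section 7.2 puts the CDAI remission limit (<10) above the SDAI remission limit (<3.3), although it describes CDAI as SDAI without the laboratory item

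*Protocol*

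**What the plan says.** Section 7.2 of the protocol (Medical record) has the rheumatologist examine the patient and "apply clinical evaluation indices such as" DAS28, SDAI, CDAI and HAQ-DI.

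- **SDAI** has five items: swollen joints, tender joints, a pain scale, a laboratory marker and the patient's global status. On its range: "The total score can range from 0 to 86". On its limits: "values above 26.0 indicate high disease activity, while values below 3.3 reflect disease remission".
- **CDAI** is defined by reference to SDAI: "The CDAI is similar to the SDAI, but differs in that it does not include laboratory measurements". It is "calculated by adding the following parameters: number of swollen joints, number of tender joints", the pain scale and the patient's overall condition. On its range: "The total score ranges from 0 to 76". On its limits, introduced as being like those of SDAI: "values less than 10 indicate disease remission, while values greater than 22.0 indicate high disease activity".

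No low or moderate band is given for either index, and no other section restates or corrects these limits.

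Elsewhere, specific objective 4 (section 4 b) is to compare clinical activity before and after supplementation, without naming an index. Section 6 h lists DAS28 as the only composite activity index among the dependent variables, and section 6 d uses DAS28 for eligibility.

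**The concern.** Two indices may have different limits without any error. The difficulty here is the direction. On the protocol's own description CDAI is SDAI with one item removed, so a patient's CDAI should be no higher than her SDAI. The high-activity limits respect that order. The remission limits do not: the index with fewer items is allowed the higher score.

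If both indices were categorised as written, a group of patients would receive contradictory labels from the same visit, and remission would look more frequent, or at least no less frequent, by CDAI than by SDAI purely because of the limits. If the discrepancy were noticed only after unblinding, someone would have to choose a limit with the results in view.

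**Working it through.** **Inputs, all from protocol section 7.2**

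| | SDAI | CDAI |
|---|---|---|
| Items | five, one of them laboratory | the four non-laboratory items, added |
| Range | 0–86 | 0–76 |
| Remission | < 3.3 | < 10 |
| High activity | > 26.0 | > 22.0 |

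**Step 1. Do the stated ranges fit a common sum?** Assume 28 joints for each count (section 7.2 states 28 for DAS28 only) and 0–10 for the pain and global scales.

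- CDAI maximum: 28 + 28 + 10 + 10 = 76, which is the stated figure.
- Left for the laboratory item: 86 − 76 = 10.

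The ranges are therefore consistent with SDAI = CDAI + L, where L is the laboratory contribution and L ≥ 0. It follows that CDAI ≤ SDAI for the same patient at the same visit.

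**Step 2. What laboratory contribution would line up each pair of limits?** Take the SDAI limit minus the CDAI limit.

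- High activity: 26 − 22 = +4. This lies within 0 to 10, so the pair is compatible with the definition.
- Remission: 3.3 − 10 = −6.7. A non-negative item cannot supply this, so the pair is not compatible.

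**Step 3. What happens to the labels?**

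- SDAI < 3.3 implies CDAI ≤ SDAI < 3.3 < 10. Every patient in SDAI remission is also in CDAI remission.
- 3.3 ≤ CDAI < 10 implies SDAI = CDAI + L ≥ 3.3. The patient is in CDAI remission and cannot be in SDAI remission, whatever the laboratory result.

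The disagreement runs one way only, so remission by CDAI can never be less frequent than remission by SDAI.

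**Illustration (invented patient).** One swollen joint, two tender joints, pain 2 and global 2 give CDAI = 1 + 2 + 2 + 2 = 7, which is remission under the CDAI sentence. Her SDAI is 7 + L ≥ 7, which is not remission under the SDAI sentence.

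**The case against.** The best reply is that nothing in the plan depends on these limits. DAS28 is the only activity index in section 6 h and the only one used for entry in section 6 d. The sample size in section 6 g rests on serum vitamin E. Objective 4 names neither an index nor a category, and no CDAI or SDAI remission analysis is planned. All of this stands, and it fixes the rank of the point as minor.

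A second reply is that the ordering argument needs an assumption. Section 7.2 says that CDAI is obtained by adding, but says only that SDAI is based on its five parameters. Leaving 10 points for the laboratory item also sits awkwardly with raw ESR in mm/hr or CRP in mg/l (the units in section 6 h), since neither is obviously capped at 10. Some unstated scaling may be needed. This is fair, and the assumption must be declared. It does not rescue the limits, because any non-negative contribution added to the four CDAI items, however scaled, still gives CDAI ≤ SDAI.

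A third reply is that the indices are introduced as examples in a descriptive section. They are nevertheless what the rheumatologist is told to apply, and the limits are the protocol's own rules for reading the scores. An error in them is an error in this document, not a detail left to the analysis plan.

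**Conclusion.** The point holds as a minor internal inconsistency that is wrong as written. Section 7.2 sets the CDAI remission limit 6.7 points above the SDAI limit, while its high-activity limits run 4 points the other way. For CDAI from 3.3 to just under 10 the two remission labels cannot agree. This rests on SDAI being a sum like CDAI and on a laboratory item that is not negative. The first is assumed, though the stated ranges fit it.

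The effect is confined to CDAI or SDAI categories, should any be reported under objective 4. The continuous CDAI and SDAI scores, the DAS28 variable, eligibility and sample size are untouched.

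Three stronger readings are not supported:

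- A reader might infer that the limits conflict because they sit at different shares of their ranges (3.3/86 = 3.8% against 10/76 = 13.2%). Nothing requires equal shares. By that test the DAS28 remission limit in the same section (2.6 on a stated 0–10 scale, 26%) would conflict with SDAI too.
- A reader might take the width of the 3.3-to-10 band, or the number of score values in it, as the proportion of patients mislabelled. The protocol gives no distribution of scores, so that proportion is unknown.
- A reader might conclude that the CDAI limit is the faulty one. The documents show only that the two sentences are incompatible, not which limit or label is at fault.

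**What to change.** Check the CDAI and SDAI remission limits in section 7.2 against the source instruments and reconcile them, so that they are compatible with CDAI being SDAI without its laboratory item. Do this before unblinding and before any CDAI or SDAI category is assigned or reported. No replacement value is proposed here, because the protocol does not contain the means to choose one.

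The cost is a wording change in section 7.2. No new measurement is needed, and eligibility, the DAS28 variable and the sample size stay as they are. Scores already collected remain usable, because the limits enter only when categories are assigned.

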7.4 Supplementation

Study participants with vitamin E deficiency, as determined by a 24-hour recall, will receive either 800 mg of α -tocopherol in capsules daily, divided into two 400 mg doses (one after breakfast and one after lunch), or a placebo consisting of 200 mg of magnesium oxide. Both the supplement and placebo will be packaged identically to ensure double-blinding, preventing both participants and researchers from knowing the treatment assignment. In addition, each participant will be given a diary to assess treatment adherence, as detailed below.

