This project is a randomized, double-blind clinical trial that aims to supplement RA patients with vitamin E insufficiency with vitamin E for one month and evaluate the effect of vitamin E on clinical activity and inflammation in these patients. The risk is considered greater than minimal due to the use of randomized methods for assigning patients to vitamin E supplementation or placebo. This decision is based on the need to ensure the rigor and objectivity of the study. It is important to note that to date, no harmful interactions between vitamin E and standard RA treatment, which is based on DMARDs, glucocorticoids, and NSAIDs, have been reported, according to the PubMed, UpToDate, Drugs.com, and DrugBank platforms.

The suggested dose for supplementation is 800 mg/day is based on previous clinical trials that have demonstrated its potential anti-inflammatory effect and decreased RA activity. In addition, a study conducted by Dysken MW et al. in 2014 evaluated the safety of vitamin E for one year and no adverse effects were observed with supplementation. The supplement intended to be used is Tocofersolan (α -tocopherol), which has health registration with COFEPRIS (006V2002 SSA) and is manufactured by Gelpharma, SA de C. V (The researchers declare no conflict of interest). This supplement will be covered by the researchers. Supplementation of patients with vitamin E capsules will be from the same batch to ensure consistency, reproducibility, and validity of the results.

Based on the above, we are interested in determining whether supplementation with Vitamin E (α -tocopherol) for one month has effects on clinical activity and inflammation in patients with RA from Western Mexico.

4. Objectives

a. General objective

Evaluate the effects of supplementation with Vitamin E (α -tocopherol) in patients with RA, as well as its relationship to clinical activity and inflammation of the disease.

b. Specific objectives

1. To analyze the clinical characteristics and diet quality of patients with RA
2. To determine serum levels of autoantibodies in patients with RA
3. To quantify serum vitamin E levels before and after supplementation in both study groups (vitamin E and placebo)
4. To compare clinical activity before and after supplementation in both study groups
5. To quantify the serum concentration of the proinflammatory cytokines IL1 β , IL6 and TNF- α before and after supplementation in both study groups

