6. To determine the antioxidant capacity before and after supplementation in both study groups
7. To associate vitamin E levels with clinical and inflammatory parameters in patients with RA

5. Hypothesis

There is an association between supplementation with Vitamin E (α -tocopherol) and the decrease in clinical activity and inflammation in patients with RA from Western Mexico

6. Methodological design

a) Type of study

- Randomized, controlled, double-blind clinical trial.
- Randomization: Simple randomization will be performed. The study will consist of two groups: control and intervention. Participants will be randomly assigned using a random selection process, using the OxMaR system (an acronym for Oxford Minimization and Randomization), a validated software. Randomization will be performed by a researcher independent of the project.
- Definition of patients:
- Female patients with RA will be included due to the prevalence and characteristics of the disease: a higher incidence in women and differences in clinical presentation, as they tend to present more severe signs and symptoms. Furthermore, the influence of hormonal factors is considered, given that female sex hormones have a significant impact on the modulation of the immune system. The study also seeks to improve the validity and applicability of the results through sample homogeneity, which reduces variability in treatment response associated with sex-related hormonal and genetic factors.
- Patients with vitamin E deficiencies (<15 mg/day) who are receiving conventional synthetic DMARDs (methotrexate, hydroxychloroquine, leflunomide, sulfasalazine, and their combinations) for more than one month. The intervention group will receive vitamin E at a dose of 800 mg/day, divided into two doses of 400 mg each. The control group will receive a magnesium oxide placebo at a dose of 200 mg/day. Participants will consume one capsule of vitamin E or placebo after their morning and evening meals.
- Patients receiving glucocorticoids will not be included, as current clinical guidelines advise against prolonged use of glucocorticoids, especially at high doses, and recommend limiting them to short-term bridging therapy in specific cases. Furthermore, it is suggested that treatment with these drugs may mask symptoms such as joint pain and decrease inflammatory parameters (acute phase reactants and proinflammatory cytokines).

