- Use of placebo: Participants will be informed that they could be taking either vitamin E or placebo. Both vitamin E and placebo will have similar excipients and will be masked by similar packaging.
- Double-blinding: To minimize bias in the study, it is important that both the researchers involved and the participants be blinded as to who is receiving the active treatment and who is receiving the placebo. Once the one-month supplementation period and data collection are

over, the study will be unblinded. A researcher independent of the project will maintain the double-blinding information.

- During the study, potential adverse events will be identified through scheduled consultations and spontaneous reports from participants, who will have access to a 24-hour communication channel. All events will be recorded in a standardized format (Naranjo Questionnaire and Adverse Event Recording Form), evaluated by the principal investigator or a safety committee, and classified according to their severity and relationship to treatment. Mild or moderate events will receive symptomatic treatment, while severe events will be reported to the appropriate authorities, with treatment suspension if necessary. Each affected participant will be monitored until the event is completely resolved, ensuring their safety and an appropriate response at all times.

b) Research venues

- Institute for Research in Biomedical Sciences (IICB) of the University Center for Health Sciences (CUCS)
- Clinical Analysis and Translational Research Laboratory (LACIT), at the University Center for Exact Sciences and Engineering (CUCEI)
- Rheumatology Service of the “Fray Antonio Alcalde” Civil Hospital in Guadalajara, Jalisco.

c) Study period

November 2024 to January 2027.

d) Inclusion criteria

Female sex, RA classification (ACR/EULAR 2010), early RA \leq 2 years, treatment with conventional synthetic DMARDs (methotrexate, hydroxychloroquine, leflunomide, sulfasalazine and their combinations) for more than one month, DAS28 \geq 3.2, vitamin E deficiency (<15 mg/day), no comorbidities: arterial hypertension, type 2 diabetes, dyslipidemias, severe interstitial lung disease, active or recent cancer (less than 5 years in remission), chronic infections (active tuberculosis, hepatitis B or C, HIV), age $>$ 18 years, voluntary participation and signing of informed consent.

e) Exclusion Criteria

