Liver and kidney diseases, overlap syndrome with other autoimmune diseases, coagulation disorders, pregnancy, consumption of supplements (iron, vitamin E and/or K), and medications such as aspirin, amlodipine, estrogens, glucocorticoids and medications used in the treatment of dyslipidemia in the last three months.

f) Elimination Criteria

Errors in supplement administration $\geq 20\%$: The treatment adherence form (Annex 14) will be used as the tool to be used, recording daily vitamin/placebo intake. Patients who fail to consume at least 80% of the total daily intake (48 capsules) will be eliminated from the study. Patients with adverse effects from the supplement (Annexes 15 and 16), pregnancy during the study, insufficient blood sample collection, and voluntary withdrawal of informed consent may be excluded.

g) Sample Size

The two-means statistical formula was used to calculate the sample size. To do this, the following data are required: Identify whether the hypothesis is unilateral or bilateral. Establish alpha and beta levels, and use them to determine the K value ($Z\alpha$ and $Z\beta$). The difference in measurements we would expect to find or want to be able to detect in our study ($\mu_1 - \mu_2$), the expected standard deviation for each group .

Calculations were performed using data from the 2001 clinical trial by Mona Helmy et al., resulting in a sample size of 19 patients plus a 20% increase to cover potential losses.

Data: Serum vitamin E levels: start: 0.64 mg/dL and end: 0.86 mg/dL

K value: 15.8 with a statistical power of 95%.

Standard deviation of vitamin E levels: start: 0.16 mg/dL and end: 0.18 mg/dL

Twenty-three patients were included in the control and intervention groups. Both groups had RA from the Rheumatology Service of the “Fray Antonio Alcalde” Civil Hospital in Guadalajara, Jalisco.

$$n = \frac{K(\sigma_1^2 + \sigma_2^2)}{(\mu_1 - \mu_2)^2}$$

Formula substitution:

$$n = \frac{15.8(0.16^2 + 0.18^2)}{(0.86 - 0.64)^2} = 18.93$$

$18.93 + 20\% \text{ in case of loss} = 22.7 = \mathbf{23 \text{ patients per group}}$

h) Variables

Independent variables

- Vitamin E

Dependent variables

- Inflammatory cytokines (IL-1 β , IL-6, and TNF- α). Antioxidant capacity (DPPH, ABTS, FRAP, and ORAC). Clinical course: DAS-28. Acute phase reactants: pCr and ESR. Autoantibodies: Anti-CCP and Rheumatoid factor.

Operationalization of variables			
Variable	Interrelationship	Nature	Indicator

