The supplement intended to be used is Tocoferosolan (α -tocopherol), which has health registration with COFEPRIS (006V2002 SSA) and is manufactured by Gelpharma, SA de CV, while the placebo is manufactured by Botica Toledo and will contain 200mg of magnesium oxide.

The researchers responsible for this project declare that there are no conflicts of interest related to the objectives, methodologies, or results of this study. No member of the research team has any financial, commercial, or personal interests that could influence the conduct, interpretation, or presentation of the project results.

j) Ethical considerations

The project will be conducted in accordance with the ethical standards and principles for medical research involving human subjects, as set out in the Declaration of Helsinki, last revised at the 64th General Assembly in Fortaleza, Brazil, in October 2013. The Declaration also refers to the ethical principles for medical research involving human subjects.

Participation of subjects included in the study will be voluntary, with prior signing of the informed consent letter (Annex 14) prepared in accordance with the provisions of guidelines 9, 10 and 12.

- Guideline 9: Equitable inclusion of research participants, ensuring that the benefits and risks of research are distributed fairly among all groups involved.

- Guideline 10: Respect for informed consent, ensuring that this process is understandable, voluntary, and appropriate to the cultural and social context of the participants.

Guideline 12: Ensure that research involving vulnerable participants is conducted fairly and ethically, avoiding any type of abuse, and ensuring that these groups receive equal rights.

As well as Appendix 2 (which guarantees fair, safe, and respectful treatment of all participants) of the guidelines developed by the Council for International Organizations of Medical Sciences (CIOMS), Title Two of the General Health Law on Health Research, Articles 21 (research on human beings may only be carried out when the human rights of the subjects are respected), and 22 (informed consent is essential for entering the protocol and must be given freely and voluntarily). Individual treatment of each patient will be the same for all, always with respect and protection of their integrity. Participation in this study will not generate any cost for the patient, and only the essential resources to carry out this project will be used.

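### The placebo is magnesium oxide, not justified as inert and with an inconsistent stated amount, and nothing requires the capsules of the two arms to match

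*Protocol*

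**What the plan says.** Three places give the content of the control capsule, and all name magnesium oxide:

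- Section 6 a), Type of study: "The control group will receive a magnesium oxide placebo at a dose of 200 mg/day". The same paragraph sets two capsules a day in both arms: "Participants will consume one capsule of vitamin E or placebo after their morning and evening meals".
- Section 6 i), Biosecurity considerations: the placebo "will contain 200mg of magnesium oxide". This passage also names a different manufacturer for each product.
- Section 7.4, Supplementation: "or a placebo consisting of 200 mg of magnesium oxide", with no statement of whether this is per capsule or per day.

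No section gives a reason for choosing magnesium oxide or says that it is inert at the amount used. The interaction statement in section 3 concerns vitamin E only: "no harmful interactions between vitamin E and standard RA treatment, which is based on DMARDs, glucocorticoids, and NSAIDs, have been reported".

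Masking of the products is described twice. Section 6 a) says "Both vitamin E and placebo will have similar excipients and will be masked by similar packaging". Section 7.4 says "Both the supplement and placebo will be packaged identically to ensure double-blinding". Section 6 a) also has an independent researcher randomise and an independent researcher hold the code.

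**The concern.** The hypothesis in section 5 credits any fall in clinical activity and inflammation to vitamin E. That needs a control that differs from the active capsule only by lacking vitamin E. Here the control has its own named compound, a mineral oxide that the protocol does not list for the vitamin E capsule. The arms therefore differ in two substances, and the arm difference cannot strictly be assigned to one of them.

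The second issue is the blind. Participants handle the capsules twice a day for a month. Identical boxes do not conceal capsules that look or smell different, and the products come from two makers. If participants can tell the arms apart, the outcomes that rest on their own report can shift for reasons unrelated to vitamin E. Neither problem can be repaired by analysis once the data are in.

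**Working it through.** **Number of capsules.** Section 6 f) sets 48 capsules as 80% of intake, so the full course is 48 / 0.80 = 60 capsules. At two a day that is 30 days, which agrees with the one-month period.

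**Group size.** Section 6 g): 15.8 × (0.16² + 0.18²) / (0.86 − 0.64)² = 15.8 × 0.0580 / 0.0484 = 18.93. Then 18.93 × 1.2 = 22.7, so 23 per group, as stated. This calculation uses serum vitamin E and contains no term for the control substance, so the present point does not change it.

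**Amount of magnesium oxide under each reading.** The magnesium fraction by molar mass is 24.3 / 40.3 = 0.603. This is ordinary chemistry, not a figure from the protocol.

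| Reading | Per capsule | Per day | Over 60 capsules | Magnesium per day |
|---|---|---|---|---|
| 200 mg is the daily amount (6 a) | 200 / 2 = 100 mg | 200 mg | 6 g | 200 × 0.603 ≈ 121 mg |
| 200 mg is the content of one capsule (possible reading of 6 i) and 7.4) | 200 mg | 200 × 2 = 400 mg | 12 g | 400 × 0.603 ≈ 241 mg |

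The readings differ by a factor of two. The protocol does not settle which applies, and the three places must be reconciled.

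**What the masking text covers.** The two statements together cover excipients (similar) and packaging (similar in 6 a), identical in 7.4). Section 6 a) already equalises the number of capsules per day. Neither statement, nor any other section, requires the capsules to match in shell, size, colour or smell. No check of blinding is described.

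**Which outcomes are exposed** (7.2 Medical record; 7.4.2 to 7.4.8):

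- Reported by the participant: the visual analogue pain scale (in DAS28, SDAI and CDAI), patient global status (SDAI and CDAI) and HAQ-DI.
- Elicited by the rheumatologist but dependent on the participant's response: the painful-joint count.
- Hardly open to a participant's guess: ESR, CRP, cytokines, autoantibodies, antioxidant capacity and serum vitamin E.

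Two of the four DAS28 inputs (pain scale and painful joints) are therefore exposed to some degree.

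**Size of any bias.** The protocol gives no effect of magnesium oxide on any outcome and no rate of correct guessing. Neither the size nor the sign of a bias can be computed.

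**The case against.** The strongest reply is that a biased contrast has not been shown. That magnesium oxide has activity of its own is general pharmacology and not in the protocol. A mass of magnesium shows how much is given, not that it does anything to DAS28 or cytokines. The protocol also has real safeguards: independent randomisation, an independently held code, similar excipients, equal capsule numbers, and a stated aim of keeping participants and researchers unaware. All of this stands, and it limits the point to an unjustified comparator and an unstated match.

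Four stronger readings are tempting, and the documents do not support them:

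- *Each control capsule holds 200 mg.* This is one reading only; section 6 a) implies 100 mg.
- *The capsules look different, or the blind is broken.* No section describes the appearance or fill of either capsule. The protocol fails to require a match; it does not show a mismatch.
- *The whole trial is open to unblinding bias.* The laboratory outcomes carry much of the inflammation objective and are hardly affected by a participant guessing her arm.
- *Magnesium should have been in the exclusion list.* The list covers "consumption of supplements (iron, vitamin E and/or K") and omits magnesium, but outside intake is a background factor that randomisation spreads over both arms. It creates no systematic difference.

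A further fair objection is timing. The Summary and section 6 g) describe recruitment in the past tense, while section 6 a) uses the future, so enrolment status is uncertain. If participants have been dosed, changing the filler would split the control arm between two comparators.

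**Conclusion.** The point holds as a design weakness worth correcting. As written, the trial compares vitamin E with magnesium oxide, without a statement that the latter is inert. The control amount is ambiguous by a factor of two (200 or 400 mg a day; about 121 or 241 mg of magnesium). Capsule matching is left open where several clinical measures depend on the participant's report.

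The consequence is a possible bias of unknown size and direction in the clinical-activity comparison, and an arm difference that cannot be attributed to vitamin E alone. It is not a demonstrated bias. The conclusion assumes that the vitamin E capsule contains no comparable magnesium oxide, since none is stated, and that the protocol text is the full specification of the two products.

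**What to change.** **If no participant has been dosed:** amend 6 a), 6 i) and 7.4 Supplementation so that the placebo is an inert filler based on the carrier and excipients of the vitamin E capsule. Require the capsules themselves, not only the packaging, to match in shell, size, colour and smell. This also removes the ambiguity over the amount. The cost is one small batch (23 × 60 = 1,380 capsules before spares), an amendment that may need committee review, and a short delay.

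**If participants have already been dosed:** keep a single comparator. Reconcile 6 a), 6 i) and 7.4 so that they state one amount and its basis. Name the control as magnesium oxide in the report and its conclusions, and state whether the capsules matched. At one month, before unblinding, ask each participant which capsule she thinks she took, and tabulate the answers by arm. Guesses can also reflect perceived benefit, so the table informs interpretation and does not by itself prove that the blind failed. The cost is one question per participant and a short text amendment.
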